SLUMBER, every unit provides baseline and follow-up data. We will collect baseline data just prior to the intervention on a given unit and within 1 month after a 3-month exposure to the SLUMBER program. Facilities will encourage staff to continue to use intervention approaches after the 3-month intervention period. We will collect additional follow-up sleep and activity data with resident surveys and repeat wrist actigraph measures 3 and 6 months after the post-intervention period for all units to test for increased or continued benefit (sustainment) over time and assess for the possibility of reduced benefits over time (relapse). **From the intervention beginning and throughout the remaining study duration, real-time environmental data (noise via decibel meters) and observed sleep disturbance (by staff anonymous recording of sleep disturbances) will be available to SNF staff on a visible computer interface (described below) to facilitate continued use of SLUMBER strategies.** MDS 3.0 data collection will provide repeated measures of mood, cognitive function, and physical function for the full study duration (Figure 3). We selected a 3-month follow-up time point to strike a balance between sufficient time for intervention effects to emerge while considering the rapidly changing health status of LTC residents. Also, MDS data are collected quarterly and the intervention itself includes an initial mentoring session, three additional meetings over the next two months, and a follow-up session at the end of three months.

Supplement Design:

1. Overview: For this supplement application, we propose a 12-month intervention trial focused on dementia care SNF units using a modified comprehensive sleep improvement program, SLUMBER-RD, which is a mentored approach for unit staff. The study will be conducted in two urban SNFs with the goal of enhancing sleep quality, mood, cognitive performance, and activity engagement.

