Analysis of Scheduled Study Assessments: Mixed-effects models will be used to assess improvement in sleep outcomes due to the SLUMBER intervention. When applied to repeated measures designs, mixed-effects models accommodate incomplete data across time points (e.g., due to resident death) and can permit specification of a wide variety of residual covariance structures.¹⁰³ Each outcome will be analyzed using a two-level mixed-effects model with time as a fixed factor having four levels (baseline, post-intervention, 3-months, and 6-months), and residents nested within SNF units. We will also conduct a sensitivity analysis that takes into account nesting of units within facilities. Non-independence of residuals across time will be modeled using a variety of covariance structures (e.g., unstructured, compound symmetric, autoregressive) by selecting the covariance structure that provides the best fit (according to the Bayesian Information Criteria). We will assess the primary hypothesis concerning the intervention effect by comparing the average baseline score to the average post-intervention and 3-month scores. We will test the secondary hypothesis concerning withdrawal of the intervention by comparing the 3-month to 6-month data.

Analysis of Routinely Collected Measures: Routinely collected measures (for all consented residents on intervention units) will be analyzed using a three-level model in which time is nested within resident and residents are nested within SNF units.¹⁰⁴ A sensitivity analysis will consider a model in which a fourth level of

Level 1 (time) Outcome _{ijk} = $\pi_{0jk}+\pi_{1jk}(\text{Intv})+\pi_{2jk}(\text{IntvQtr})+e_{ijk}$	units nested within facilities is considered. The three-level model will include two key time varying predictors: Intv ,

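### The withdrawal test for the scheduled assessments compares 3-month with 6-month data, both collected after the intervention has ended; no named contrast tests change from post-intervention to 3 months

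*Combined protocol and SAP*

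**What the plan says.** C6, Analysis of Scheduled Study Assessments, fits a mixed model with "time as a fixed factor having four levels (baseline, post-intervention, 3-months, and 6-months". It names two contrasts. The primary hypothesis is assessed by "comparing the average baseline score to the average post-intervention and 3-month scores". The second reads: "We will test the secondary hypothesis concerning withdrawal of the intervention by comparing the 3-month to 6-month data".

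A5, Study Design, fixes the visits. Post-intervention data are collected "within 1 month after a 3-month exposure to the SLUMBER program". Resident surveys follow, with "repeat wrist actigraph measures 3 and 6 months after the post-intervention period for all units". Their stated purpose is "to test for increased or continued benefit (sustainment) over time and assess for the possibility of reduced benefits over time (relapse".

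C1 (Steps D, E and F) has the intervention delivered over three months with five mentoring sessions. C2 (Unit Meetings) puts the last session at the end of that period.

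The text is less clear about what support continues:
- C2 (Use of Technology) ties staff messaging to the mentors to the three-month period.
- C2 (Intervention monitoring and follow-up) lists monthly team meetings and web office hours with no end date.
- A5 has facilities encourage staff to carry on, and it keeps the data display running: "From the intervention beginning and throughout the remaining study duration, real-time environmental data (noise via decibel meters".

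For the MDS measures only, C6 (Analysis of Routinely Collected Measures) adds removal terms, RemInt and RemIntQtr, meant to capture deterioration once the intervention ends.

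**The concern.** A test of withdrawal should compare a visit at the point of withdrawal with a later one. Here both visits come later. Nothing in the readable text describes anything being withdrawn between the 3-month and 6-month visits. The contrast therefore misses any loss that is complete, or has levelled off, by the 3-month visit. It sees only part of a gradual loss. It does see loss that starts after the 3-month visit.

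The primary contrast does not fill the gap. It averages the post-intervention and 3-month visits, so an early loss dilutes the estimate without being tested.

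At stake is the purpose A5 gives for the follow-up visits. A null 3- versus 6-month result could be read as evidence that ending the program did no harm, when the benefit had already gone. The plan also places removal differently in its two data streams: at the end of the intervention for the MDS measures, and three months or more later for the scheduled assessments.

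**Working it through.** **1. The plan's own figure.** Table 6 gives detectable effects for the primary contrast only; the withdrawal contrast has no stated power. Table 6 can be reproduced with a stepped-wedge generalized least squares variance: six units staggered by one period, each observed in three periods (baseline untreated, post-intervention and 3-month treated), and the effect scaled by the within-unit SD. All 25 cells agree to within 0.01 SD. For example, ICC 0 with n = 10 gives 0.498 against 0.50, and ICC 0.40 with n = 18 gives 0.598 against 0.60.

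**2. Timeline, in months from the start of the intervention (A5, C1).**

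| Event | Month |
|---|---|
| Baseline | 0 |
| Intervention ends | 3 |
| Post-intervention visit | about 3 to 4 |
| 3-month visit | about 6 to 7 |
| 6-month visit | about 9 to 10 |

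The nine-month span for four assessments in C3 fits this.

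**3. What each contrast returns.** Effects are in SD relative to baseline. Primary = (post + 3-month)/2. Planned withdrawal = 6-month − 3-month. Missing contrast = 3-month − post. The starting value 0.60 is the effect size used in C6. The patterns are illustrative, and no variance, correlation or ICC enters.

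| Post / 3-month / 6-month | Primary | 6-month − 3-month | 3-month − post |
|---|---|---|---|
| 0.6 / 0.6 / 0.6 | 0.60 | 0.00 | 0.00 |
| 0.6 / 0 / 0 | 0.30 | 0.00 | −0.60 |
| 0.3 / 0.3 / 0.3 | 0.30 | 0.00 | 0.00 |
| 0.6 / 0.3 / 0.3 | 0.45 | 0.00 | −0.30 |
| 0.6 / 0.3 / 0 | 0.45 | −0.30 | −0.30 |
| 0.6 / 0.6 / 0 | 0.60 | −0.60 | 0.00 |

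Rows 2 and 3 agree on both named contrasts and differ only on the missing one. The last row shows the reverse: only the planned contrast sees late loss. Both are needed.

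**4. Illustrative power.** Assumptions, none from the documents: exponential decay from 0.60 SD, between-visit correlation ρ of 0.3 to 0.7, no unit-by-time variance, no natural decline. From Table 5, 10 to 18 residents in each of six units gives n = 60 to 108. The unit intercept cancels, so SE = √(2(1 − ρ)/n), tested two-sided at 0.05.

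Worked case: n = 84, ρ = 0.5, half-life three months from the post visit (0.60 / 0.30 / 0.15). SE = √(1/84) = 0.109. The 3- versus 6-month change of 0.15 has 28% power. The post versus 3-month change of 0.30 has 79%.

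| Decay assumption | 3- versus 6-month | Post versus 3-month |
|---|---|---|
| Half-life 1 month, from post visit | 7–14% | 93–100% |
| Half-life 3 months, from post visit | 17–52% | 50–98% |
| Half-life 3 months, post visit 1 month into decay (0.476 / 0.238 / 0.119) | 12–36% | 34–89% |
| Half-life 6 months, from post visit | 12.9–38.5% | 21.0–65.5% |

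**5. Natural decline.** Suppose the effect is constant and residents decline by an assumed 0.10 SD per three months. Both follow-up contrasts then return −0.10. Neither separates decline from loss of effect.

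**The case against.** The best defence is the goal in A2, which claims benefit as far as three months of follow-up. On that reading the primary average covers the window of claimed benefit, and 3- versus 6-month asks whether benefit lasts beyond it. The fault would then be mainly the word withdrawal. This explains the primary contrast. It does not justify the label, and it leaves untested the first interval in which the relapse named in A5 could occur.

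Other points stand in part:
- **The model already estimates every visit mean.** True, and those means would tell rows 2 and 3 of the table apart. The gap is in what is pre-specified, not in what can be estimated.
- **Support may taper rather than stop.** True. The end of the mentored period is then not a clean withdrawal either. That weakens any withdrawal label without supporting one at the 3-month visit.
- **Some material is unavailable.** The design figures and the intervention manual cannot be read and the timeline table is broken, so the statement that nothing is withdrawn between the visits is limited to the readable text.
- **The power figures favour the early contrast by construction.** True: exponential decay puts more of the change in the first interval, and 0.6 / 0.6 / 0 reverses the ranking. The conclusion does not use them.

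**Conclusion.** The concern holds. The contrast called withdrawal starts about three months after the mentored intervention ends, and no named contrast covers the interval just before it. Followed as written, the plan gives 0.30 and 0.00 both for a 0.60 SD benefit entirely lost by the 3-month visit and for a 0.30 SD benefit fully sustained. This rests only on the visit timing in A5 and the contrast definitions in C6.

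The reach is limited. It concerns a secondary hypothesis for the scheduled assessments. The primary test is touched only through averaging in the 3-month visit, and the MDS model has its own removal terms. The point should be corrected before analysis, but it does not threaten the main comparison.

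Adding the contrast will not yield a clean withdrawal estimate. Some support may continue, the post visit may come up to a month after the intervention ends, and the scheduled-assessment model has no calendar-time term. A5 itself chose its follow-up time "while considering the rapidly changing health status of LTC residents", so natural decline is a real competing explanation.

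**What to change.** In C6, Analysis of Scheduled Study Assessments:

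- Pre-specify 3-month minus post-intervention as the secondary contrast for change after the mentored period ends.
- Keep 6-month minus 3-month, relabelled as later change.
- Leave the primary contrast as it is, and report the estimated mean with its interval at every visit.
- State that neither follow-up contrast is a clean test of withdrawal, for the reasons given above.

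Reconcile A5 with the C2 passages on messaging, monthly meetings, office hours and the data display, so that the plan says what support ends and when. Use that same definition to code RemInt.

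The cost is SAP wording and contrast coding, with the same four visits and the same model. The price is multiplicity: one more secondary contrast per outcome, about 19 in all (6 actigraphy + 6 PSQI and BADS + 1 BCAT + 6 observed activities), and slightly more if actigraph light exposure is included. Label these contrasts secondary and acknowledge the number. One way to contain it is to test formally only the two Hypothesis 1 outcomes (total sleep time and awakenings) and the PSQI total score, which makes three tests, and to give estimates with intervals for the rest.

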Exclusion criteria include: 1) obtunded or comatose state, 2) inability to communicate verbally, 3) inability to consent and without surrogate, and 4) non-English and non-Spanish speaking. In keeping with QI strategies, all residents will be exposed to the environmental aspects of the intervention, as these strategies represent clinically proven non-experimental behavioral strategies with no perceptible harm. Recorded (anonymous) nurse observations, actions taken and observed outcomes will include all unit residents and will be recorded using the technology system to support staff-level interventions for any resident with a sleep behavioral issue. All staff input into this system is done without resident identification.

Step C. The collection of unit-level environmental data will focus on noise levels and documentation of resident symptoms in the MDS 3.0 (described below). MDS data will be de-identified and linked through unique random numbers. Data will include the routinely collected measures (MDS 3.0) by the facility on all consented residents as well as data from scheduled evaluations by research staff of residents who have consented to participate in evaluation components that are not part of usual clinical care. We have successfully employed this type of nested design for data collection in prior research. Federally mandated MDS 3.0 data is collected by the facility for all residents at admission and quarterly thereafter. We will obtain these data covering the time period of last collection beginning just prior to the introduction of the SLUMBER intervention, and ending at the conclusion of all data collection at each study site (nursing facility unit).

Steps D, E and F will comprise the SLUMBER intervention program itself. This process will begin as soon as the sleep team is identified, and will continue in sequence. Besides a “menu” of sleep improvement procedures, we will present the **3-component SLUMBER intervention** to unit staff: **1) Improving the nighttime sleep environment; 2) Increasing patient activity levels during the day and reducing daytime behaviors that lead to sleep disturbances at night; and 3) Identifying and assisting individual residents experiencing difficulties with sleep.** We will deliver the intervention over 3 months including the provision of five mentoring sessions and data feedback, which will cover the 3-month intervention period.

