Level 2 (person) $\pi_{0jk}=\beta_{00k}+r_{0jk}$	coded as 1 if the intervention is implemented in the current (or prior) 3-month period; and otherwise coded as 0. IntvQtr will be the number of quarters since the intervention was applied. We will examine the nature of growth in the outcome as a function of IntvQtr and introduce terms to account for non-linearity as needed. The model to be fit, expressed as a 3-level model fits the "jump" in outcome due to the introduction of the intervention (via the coefficient for γ_{100}) as well as the "slope" over time due to the intervention (via the coefficient for γ_{200}). To examine the impact of removing the intervention, we will further consider a model that introduces two additional time varying covariates (not shown): RemInt coded as 1 if the intervention was removed in the current (or prior) 3-month period, and otherwise coded as 0. This accounts for any deterioration in sleep outcomes when the intervention is ended. RemIntQtr is the number of quarters since the intervention was removed, capturing the change in the slope over time. We will examine the nature of growth in the outcome as a function of RemIntQtr and introduce terms to account for non-linearity as well.
$\pi_{1jk}=\beta_{10k}$	
$\pi_{2jk}=\beta_{20k}$	
Level 3 (unit) $\beta_{00k}=\gamma_{000}+u_{000}$	
$\beta_{10k}=\gamma_{100}$	
$\beta_{20k}=\gamma_{200}$	

Table 5: Final Sample Size (per unit) as Function of Consent % and Attrition % from a 40-Subject Unit

	Consent (%)			
Attrition (%)	45%	50%	55%	60%
25%	13	15	16	18
30%	12	14	15	16
35%	11	13	14	15
40%	10	12	13	14

Table 6: Detectable standardized effect as a function of final sample size per unit and ICC size

ICC	Final Sample size (per unit)				
	10	12	14	16	18
0	0.50	0.45	0.42	0.39	.37
0.10	0.58	0.54	0.51	0.48	.47
0.20	0.65	0.60	0.57	0.55	.53
0.30	0.69	0.65	0.62	0.59	.57
0.40	0.75	0.70	0.66	0.63	.60

the number of participants in the unit, 2) the consent rate, and 3) the attrition rate. Using the expected unit size of 40, Table 5 shows the final sample size as a function of consent and the attrition rates. These final sample sizes (per unit) are used in the following power calculations (which assume six units, 80% power, alpha of .05, and 2-tailed tests).

Power Analysis of Scheduled Study Assessments: For the analysis of the scheduled study assessments, the primary analysis will test the average of the outcome at baseline versus post-treatment and 3-months. The

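### The MDS model's exposure coding, taken literally, switches exposed quarters back to 0; if exposure stays on, the main model is sound but the further withdrawal model is collinear on the plan's 3-month timing

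*Combined protocol and SAP*

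**What the plan says.** All of the following is from section C6, Analysis of Routinely Collected Measures, unless noted.

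- Intv is "coded as 1 if the intervention is implemented in the current (or prior) 3-month period", with 0 in every other quarter.
- IntvQtr counts quarters from launch. Whether the count starts at 0 or 1 is not stated.
- The displayed three-level model contains an intercept, Intv and IntvQtr. Its two coefficients are described as the jump at introduction and the slope afterwards.
- A further model, to be considered for the effect of removing the intervention, adds RemInt, "coded as 1 if the intervention was removed in the current (or prior) 3-month period, and otherwise coded as 0", and RemIntQtr, which "is the number of quarters since the intervention was removed, capturing the change in the slope over time".
- C1 (Steps D, E and F) fixes the duration: "We will deliver the intervention over 3 months including the provision of five mentoring sessions and data feedback". C1 (Step C) says that MDS data are collected quarterly.
- C6, Power Analysis for Routinely Collected Measures, gives the primary comparison as the average of all measures before implementation against the average of all measures after it. Table 7 gives the detectable effects.

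**The concern.** The parenthesis about the prior period can mean the one preceding quarter or any earlier quarter, and the two meanings give different analyses. Under the first, quarters in which a unit has already been exposed are pooled with its pre-intervention quarters. The estimated jump is then diluted, and the linear term absorbs the difference as a spurious trend. Under the second, the main model behaves, but the withdrawal model may contain a redundant column. Software would then drop a term by its own rule, and the reported removal effect would depend on which term went.

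This is the specified analysis for the PHQ-9, the Pain Assessment Interview, the BIMS and the ADL measure. Section A5 names loss of benefit over time as something the study wants to detect.

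**Working it through.** **1. What exposure does Table 7 assume?** Inputs from C6: six units, six steps, 80% power, two-sided alpha .05. Assumed: one baseline quarter, so I = 6 units and T = 7 periods. The stepped-wedge (Hussey-Hughes) variance is

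Var = Iσ²(σ² + Tτ²) / [(IU − W)σ² + (U² + ITU − TW − IV)τ²],

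with σ² = 1/n, τ² = ICC/(1 − ICC), U the number of exposed cells, and W and V the sums of squared column and row totals. The detectable effect is 2.80·√Var.

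Permanent exposure: U = 21, W = V = 91. For n = 10 and ICC .20, σ² = .1 and τ² = .25, so Var = 1.11 / (3.5 + 35) = .0288 and the effect is .476. Table 7 prints 0.48. All nine cells reproduce:

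| ICC | n=10 | n=15 | n=20 |
|---|---|---|---|
| 0 | .367 | .300 | .259 |
| .20 | .476 | .391 | .340 |
| .40 | .481 | .394 | .342 |

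Exposure lasting only two quarters: U = 11, W = V = 21. The same cell gives Var = 1.11 / (4.5 + 77.5) = .0135 and an effect of .33, not 0.48. At ICC 0 it gives .32, not 0.37. Table 7 therefore rests on exposure that stays on.

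**2. The columns for one unit**, with removal one quarter after launch and both counters starting at 0:

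| Quarter since launch | pre | 0 | 1 | 2 | 3 |
|---|---|---|---|---|---|
| Intv, literal | 0 | 1 | 1 | 0 | 0 |
| Intv, stays on | 0 | 1 | 1 | 1 | 1 |
| IntvQtr | 0 | 0 | 1 | 2 | 3 |
| RemInt, stays on | 0 | 0 | 1 | 1 | 1 |
| RemIntQtr | 0 | 0 | 0 | 1 | 2 |

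**3. Cost of the literal coding.** Two designs are assumed. With one launch per quarter over 7 quarters, the exposed unit-quarters are 6+5+4+3+2+1 = 21, of which 4+3+2+1 = 10 are coded 0. With one launch every second quarter over 13 quarters, they are 12+10+8+6+4+2 = 42, of which 10+8+6+4+2 = 30 are coded 0. The table shows the expected coefficients of the displayed model by generalised least squares when the truth is a sustained .50 SD jump with no slope (n = 14, ICC .20):

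| Design | IntvQtr starts at | Intv | False slope per quarter |
|---|---|---|---|
| 7 quarters | 0 | .41 | .14 |
| 7 quarters | 1 | .32 | .11 |
| 13 quarters | 0 | .39 | .06 |
| 13 quarters | 1 | .35 | .06 |

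With a short window per unit (1 or 2 quarters before and 4 after launch, counter from 0), 71% to 76% of the jump is recovered, that is about .355 to .38 of .50, and the false slope is .16 to .17. With the stays-on coding and the same truth, the displayed model has rank 3 of 3 and returns the full jump and a zero slope.

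**4. Rank of the withdrawal model with stays-on coding.** In every column of the table in step 2, IntvQtr = RemInt + RemIntQtr (for example 3 = 1 + 2). The dependence persists for every choice of counter start:

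| IntvQtr from | RemIntQtr from | Exact relation | Rank of 5 |
|---|---|---|---|
| 0 | 0 | IntvQtr = RemInt + RemIntQtr | 4 |
| 0 | 1 | IntvQtr = RemIntQtr | 4 |
| 1 | 0 | IntvQtr = Intv + RemInt + RemIntQtr | 4 |
| 1 | 1 | IntvQtr = Intv + RemIntQtr | 4 |

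The cause is structural: time since launch and time since removal differ by a constant one quarter. When IntvQtr starts at 1, Intv itself joins the dependence, but only in this further model. Rank 5 returns if removal is dated two quarters after launch, if the gap differs between units, or if time is kept in fractions of a quarter.

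**The case against.** The strongest reply is that the plan itself shows which reading is meant. The before-versus-after contrast, the description of a jump plus a slope, and Table 7 all fit only an exposure that stays on, and with that coding the main model is full rank and unbiased for a sustained jump. This stands. A reader might infer that the MDS intervention effect is wrong or not estimable under either reading; the documents do not support that. The literal wording is still the only operational rule given, and a programmer who follows it gets the biased result.

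Second, the collinearity sits in a model that the plan will only further consider, and no primary test uses its terms. This also stands and limits the severity.

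Third, removal is never dated. A5 keeps the noise and sleep-disturbance feedback running for the rest of the study and has staff encouraged to continue, while the scheduled-assessment analysis in C6 tests withdrawal as 3-month against 6-month data. Either could place removal later than one quarter after launch, and a two-quarter gap restores full rank. So calling the withdrawal model unfittable without qualification goes too far. But the 3-month delivery and counters in numbers of quarters are what the plan states, and on those the model fails. The plan states none of the three conditions that would restore rank.

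Fourth, under the literal coding the withdrawal model is full rank in three of the four counter conventions, given enough follow-up quarters. That is true, but it is of little use, because that coding biases the main effect.

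**Conclusion.** The point holds in two limited parts.

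- **Main model.** The written coding rule contradicts the plan's own contrast and Table 7. If followed literally, it returns 10 of 21 or 30 of 42 exposed unit-quarters to 0, and shrinks a sustained .50 SD effect to about .32 to .41 with a false slope of about .06 to .14 SD per quarter. These sizes rest on the assumed 7- and 13-quarter designs, 14 residents per unit, ICC .20 and a truly flat sustained effect. The plan's two accounts of the MDS window (full study duration in A5; per-unit collection in C1, Step C) leave the real design open. With exposure left on, the bias disappears.
- **Withdrawal model.** With exposure left on, whole-quarter time and removal one quarter after launch on every unit, it has rank 4 of 5. The removal jump and slope then cannot be separated from IntvQtr.

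Severity is moderate. The first part needs one corrected rule, and the second concerns a supplementary analysis.

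**What to change.** 1. State that Intv is 1 from the launch quarter to the end of follow-up, and that RemInt is likewise 1 in every quarter from removal onward.
2. State the removal date for analysis, the time unit (whole or fractional quarters) and the starting value of each counter. A5 (continuing feedback and use), C1 (3-month delivery) and C6 (withdrawal as 3-month against 6-month) must be reconciled first.
3. Give the withdrawal model an estimable form, in one of two ways.
   - Drop one named term. With a one-quarter gap, dropping IntvQtr or RemIntQtr gives full rank under all four counter conventions. Dropping RemInt does so only if RemIntQtr starts at 0.
   - Replace all four terms, Intv included, with indicators for quarter since launch (0, 1, 2, 3 or more; pre-launch as reference). Intv must go because the four indicators sum to it: keeping it gives 6 columns of rank 5. Pre-state the intervention effect as an average of the indicators, and withdrawal as a contrast of quarters after the defined removal date against quarters before it.

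The cost is SAP wording and, for the indicator version, one or two more parameters. One limit remains: if only the launch quarter precedes removal, no coding can separate continued build-up from the effect of removal, and the SAP should say so.
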